#### **Assessment of difference in antibody response over time:**

Difference in antibody response over time will be assessed based on log-transformed scale of GMT values at different time points (baseline vs. 7 days; baseline vs. 30 days). Paired t-test will be used to test the difference in each group over time. Two-sample t-test will be used to test difference over time between groups (2-dose girls vs. 3-dose girls; 2-dose girls vs. 3-dose women; 3-dose girls vs. 3-dose women). All of the t-test will be two-sided, at a significant level of 0.05 (Table 6-7).

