The long-term goal is to understand the memory response to HPV vaccination. Although memory responses can be detected shortly after immunization, the best approach to measure the long-lasting anamnestic response is to challenge with a booster dose years (> 5) after the original exposure.

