3.0 STUDY DESIGN AND PARTICIPANT OVERVIEW

This is a single center, interventional study to evaluate long term memory response to HPV 6, 11, 16 & 18. Memory response will be assessed by measuring seroprotection 8-10 years post Q-HPV vaccination and to challenge with a booster dose of HPV9 vaccine (Gardasil® 9, Merck Canada, Inc.) years after the original exposure to measure the long-lasting anamnestic response. This is a 3 arm study with 6 girls per group:

Group 1: girls who received 2 doses of Q-HPV vaccine at 0, 6 month schedule 8-10 years ago when they were between 9-13 years of age at the time of the first dose.

Group 2: girls who received 3 doses of Q-HPV vaccine at 0, 2, 6 month schedule 8-10 years ago when they were between 9-13 years of age at the time of the first dose.

Group 3: young women who received 3 doses of Q-HPV vaccine at 0, 2, 6 month schedule 8-10 years ago when they were between 16-26 years of age at the time of the first dose.

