## **Data Analysis Plan For Demographic/Clinical Characteristics and Serology Data**

---

**Objective:** To compare the serum antibody responses to HPV 6, 11, 16 and 18 at 7 and 30 days post-booster dose of HPV vaccine in females that received either a primary 2 or 3 dose series of Q-HPV vaccine 8-10 years ago.

**Primary testing** is to determine non-inferiority (95% CI, lower bound  $>0.5$ ) of geometric mean titer (GMT) ratios for anti-HPV 6, 11, 16, 18 for 2-dose girls compared with 3-dose girls and 3-dose women.

Co-primary endpoints are the antibody levels measured by MERCK using competitive Luminex immunoassay (cLIA) at 7 and 30 days post-booster dose of HPV vaccine.

Co-secondary endpoints are the antibody levels measured by MERCK using total IgG Luminex immunoassay (TIgG) at 7 and 30 days post-booster dose of HPV vaccine. Antibody levels measured by cLIA and TIgG at baseline will also be compared in the three groups.

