#### **Non-inferiority testing:**

To test non-inferiority, t-test will be applied to assess GMT ratios in different groups (2-dose girls vs. 3-dose girls; 2-dose girls vs. 3-dose women; 3-dose girls vs. 3-dose women) at 7 and 30 days post-booster dose of HPV vaccine. Non-inferiority will be declared if the lower bound of the 95% confidence interval (95% CI) of GMT ratios is greater than 0.5 (Table 2-3).

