Table 4. Summary of HPV seropositivity at baseline, and at 7 and 30 days post-booster dose (cLIA)

Antibodies (cLIA)	Group 1 (2-dose girls)			Group 2 (3-dose girls)			Group 3 (3-dose women)		
	n	% seropositive (95% CI)	n	% seropositive (95% CI)	n	% seropositive (95% CI)	n	% seropositive (95% CI)	
Baseline									
HPV 6									
HPV 11									
HPV 16									

HPV 18						
At 7 days post-booster dose						
HPV 6						
HPV 11						
HPV 16						
HPV 18						
At 30 days post-booster dose						
HPV 6						
HPV 11						
HPV 16						
HPV 18						

Table 5. Summary of HPV seropositivity at baseline, and 7 and 30 days post-booster dose (total IGG)

Antibodies (IGG)	Group 1 (2-dose girls)		Group 2 (3-dose girls)		Group 3 (3-dose women)	
	n	% seropositive (95% CI)	n	% seropositive (95% CI)	n	% seropositive (95% CI)
Baseline						
HPV 6						
HPV 11						
HPV 16						
HPV 18						
At 7 days post-booster dose						
HPV 6						
HPV 11						
HPV 16						
HPV 18						
At 30 days post-booster dose						

HPV 6						
HPV 11						
HPV 16						
HPV 18						

Table 6. Difference in anti- HPV GMTs between baseline vs. at 7 and 30 days post-booster dose of HPV vaccine (cLIA)

Antibodies (cLIA)	Group 1 (2-dose girls)		Group 2 (3-dose girls)		Group 3 (3-dose women)		Group 1 vs 2	Group 1 vs 3	Group 1 vs 3
	Log Difference	P Value	Log Difference	P value	Log Difference	P value	P-value for difference between differences for group 1 vs 2	P-value for difference between differences for group vs 3	P-value for difference between differences for group 1 vs 3
Baseline vs. 7 days post-booster dose of HPV vaccine									
HPV 6									
HPV 11									
HPV 16									
HPV 18									
Baseline vs. 30 days post-booster dose of HPV vaccine									
HPV 6									
HPV 11									
HPV 16									
HPV 18									

Table 7. Difference in anti- HPV GMTs between baseline vs. at 7 and 30 days post-booster dose of HPV vaccine (total IgG)

Antibodies (IGG)	Group 1 (2-dose girls)		Group 2 (3-dose girls)		Group 3 (3-dose women)		Group 1 vs 2	Group 1 vs 3	Group 1 vs 3
	Log Difference	P Value	Log Difference	P value	Log Difference	P value	P-value for difference between differences	P-value for difference between differences for group	P-value for difference between differences
Baseline vs. 7 days post-booster dose of HPV vaccine									
HPV 6									
HPV 11									
HPV 16									
HPV 18									
Baseline vs. 30 days post-booster dose of HPV vaccine									

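### No planned between-group serology comparison adjusts for the Visit 1 titre, and the rise from baseline is compared between groups by P value alone, without an estimate or confidence interval

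*SAP*

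**What the plan says.** The SAP's opening section sets the serology endpoints: "Co-primary endpoints are the antibody levels measured by MERCK using competitive Luminex immunoassay (cLIA) at 7 and 30 days post-booster dose of HPV vaccine". These are absolute levels. The non-inferiority section gives the rule: "Non-inferiority will be declared if the lower bound of the 95% confidence interval (95% CI) of GMT ratios is greater than 0.5". The rule covers three pairwise group comparisons at Day 7 and Day 30. The only other margin in the SAP is 10%, for seropositivity.

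The rise from baseline has its own section: "Difference in antibody response over time will be assessed based on log-transformed scale of GMT values at different time points". Within each group it is tested by paired t-test. For the comparison between groups the SAP says: "Two-sample t-test will be used to test difference over time between groups". Tables 6-7 hold a log difference and a P value for each group, but the between-group columns hold only P values, for example "P-value for difference between differences for group 1 vs 2".

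Baseline is not ignored. The SAP's opening section says the three groups will also be compared at baseline, and Tables 2-3 have baseline rows with GMT ratios and 95% CIs. No analysis in either document adjusts a Day 7 or Day 30 group comparison for the Visit 1 titre.

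On purpose, the protocol's introduction says that "the best approach to measure the long-lasting anamnestic response is to challenge with a booster dose years" after the original exposure. Its primary objective (section 2.0) is nevertheless cellular, comparing memory B cells and plasmablasts; serum antibody is a secondary objective. On size, section 3.0 says: "This is a 3 arm study with 6 girls per group".

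**The concern.** A post-booster titre contains antibody that was already circulating as well as antibody made in response to the booster. The three groups differ in dose number or in age at vaccination and were not randomised, so their pre-booster titres may differ. If they do, a raw post-booster ratio can move towards or away from 0.5 because of persistence rather than response. The reader of Tables 2-3 would see the imbalance but would have no post-booster ratio that allows for it.

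The analysis that does use each participant's own baseline ends in a difference-test P value. That gives the reader neither the size of the between-group difference in rise nor its uncertainty. In a trial this small, a non-significant result is likely even when the rises differ materially.

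**Working it through.** The documents give no SD, power or sample-size calculation, so there is no stated figure to reproduce.

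**Inputs**
- n = 6 per group (protocol section 3.0), so 10 degrees of freedom and t(0.975, 10) = 2.228.
- Two-sided level 0.05 (SAP, section on response over time).
- SD of the log10 rise: not stated; assumed 0.3, 0.4 and 0.5.

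**1. What a P value above 0.05 leaves open**

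CI half-width on the log10 scale = t × SD × √(2/n) = 2.228 × SD × √(2/6) = 1.286 × SD.

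| Assumed SD | Half-width (log10) | 95% CI: estimate × or ÷ | Power if true rise ratio is 0.5 | Chance of P > 0.05 |
|---|---|---|---|---|
| 0.3 | 0.386 | 2.43 | 35% | 65% |
| 0.4 | 0.515 | 3.27 | 22% | 78% |
| 0.5 | 0.643 | 4.40 | 16% | 84% |

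Power is from the noncentral t distribution with noncentrality log10(2) / (SD × √(2/6)), that is 1.74, 1.30 and 1.04. So if one group's rise were truly half the other's, the planned test would be non-significant in about 65% to 84% of such trials.

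**2. How far a baseline imbalance could move the raw ratio**

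Suppose 2-dose girls start at half the comparator's baseline titre, the response given baseline is identical, and log post-booster titre follows log baseline with slope b (all assumed).

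- Raw post-booster ratio = 0.5^b: 0.81 at b = 0.3 and 0.57 at b = 0.8.
- Fold-rise ratio = 0.5^b / 0.5 = 0.5^(b − 1): 1.62 at b = 0.3 and 1.15 at b = 0.8.

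The raw ratio falls below 1 and the fold-rise ratio goes above 1, although the groups respond identically given baseline. Under this model the ratio adjusted for log Visit 1 titre is 1. Fold rise is therefore also baseline-dependent, and it favours the group with less persisting antibody. For b below 0.5 it is further from 1 on the log scale than the raw ratio.

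**3. When the mixing is small**

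Use an additive model instead: both groups make the same amount of new antibody, the 2-dose baseline is half, and the comparator rises k-fold. The raw ratio is (0.5 + k − 1)/k, which is 0.75 at k = 2, 0.90 at k = 5, 0.95 at k = 10 and 0.975 at k = 20. A large rise leaves little room for persistence to distort the raw ratio. The corresponding fold-rise ratios are these values divided by 0.5, from 1.50 up to 1.95.

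**The case against.** The strongest reply is that the SAP already lets a reader see most of this. Baseline ratios with CIs stand next to the Day 7 and Day 30 ratios. With complete pairs, the fold-rise ratio is the post-booster ratio divided by the baseline ratio. Given an exact P value and a pooled t-test, even the CI can be recovered: a fold-rise ratio of 0.70 with P = 0.30 implies 0.34 to 1.45. This stands, and it makes the gap one of planned reporting rather than lost information. Back-calculation is still no substitute for a planned estimate, and it does not give the baseline-adjusted ratio.

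A second reply is that the post-booster level is a legitimate endpoint for the protocol's serology objective, which is to compare serum antibody responses. That also stands, and is why the raw ratio should remain primary. The protocol's background describes recall above the original peak. If the rise is many-fold, the mixing may be slight (step 3), though the documents give no expected fold rise.

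Third, the interval widths and low power come mainly from 6 per group, which no change of table alters. This is correct.

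Three stronger readings are tempting, and the documents do not support them:
- *The serology cannot address memory.* Baseline comparisons are planned, and memory is assigned first to the cellular analyses (protocol sections 2.0 and 6.2).
- *The rise from baseline isolates recall and should be held to the same 0.5 bound.* Step 2 shows that it does not isolate recall; the bound would be easier to meet for a group with poorer persistence.
- *The SAP treats P > 0.05 as similarity.* It nowhere says so, and it keeps its non-inferiority rules apart from these difference tests.

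**Conclusion.** The concern holds as a limited reporting and adjustment gap in the serology plan. The non-inferiority comparison uses raw post-booster ratios; no between-group comparison adjusts for the Visit 1 titre; and the rise is compared between groups by P value only. At assumed SDs of 0.3 to 0.5 for the log10 rise, a non-significant result leaves open ratios a factor of 2.4 to 4.4 either side of the estimate, so it would not show similar rises. The possible effect of baseline on the raw ratio (0.81 to 0.57 with half the baseline and slope 0.3 to 0.8) is illustrative: neither the imbalance nor the slope is known from the documents.

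A reader might also infer that adjustment would bring a useful gain in precision. That is not a reason for the change. In a simulation with 6 per group, log10 SD 0.4 and equal true baselines, the interval narrowed by about 7% at a correlation of 0.5 and 23% at 0.7. With one group at half the baseline, the figures were about 0% and 17%.

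**What to change.** **Tables 6-7 and the section on response over time.** Add the between-group ratio of geometric mean fold rises (Day 7 to baseline, Day 30 to baseline) with its 95% CI. Label it descriptive, attach no 0.5 bound, and note that a lower baseline tends to inflate fold rise. State that P > 0.05 is not evidence of similar rises. While editing, correct the column heads: two are labelled Group 1 vs 3, whereas the text also lists 3-dose girls against 3-dose women.

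**Tables 2-3.** Beside each raw Day 7 and Day 30 GMT ratio, add a supportive ratio with 95% CI from an ANCOVA on log titre adjusted for log Visit 1 titre. Keep the raw ratio as the primary, total-level comparison.

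**Cost.** SAP wording and table shells only; the Visit 1 sample is already in the schedule of events. The downside is one of interpretation. Baseline titre may itself be an effect of dose number in these non-randomised groups, so adjusting for it can remove part of the dose effect. The raw and adjusted ratios answer different questions, and both must be shown and labelled. Neither addition cures the imprecision of 6 per group.

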## Figures and Tables:

Figure 1. Study participation consort diagram to summarize enrollment, withdraw, loss of follow-up, eligibility...

[figure not shown]

Table 1. Demographic/clinical characteristics of the study population

Characteristics	Group 1 (2-dose girls)		Group 2 (3-dose girls)		Group 3 (3-dose women)	
	N	%	N	%	N	%
Age at enrollment, mean (SD), year						
Age at first dose of Q-HPV vaccine, mean (SD), year						
Weight, mean (SD), kg						
BMI, mean (SD)						
Ethnicity						
White						
Chinese						
Other						
Health history						
Immunization history						

**Group 1:** girls who received 2 doses of Q-HPV vaccine at 0, 6 month schedule 8-10 years ago when they were between 9-13 years of age at the time of the first dose

**Group 2:** girls who received 3 doses of Q-HPV vaccine at 0, 2, 6 month schedule 8-10 years ago when they were between 9-13 years of age at the time of the first dose

**Group 3:** young women who received 3 doses of Q-HPV vaccine at 0, 2, 6 month schedule 8-10 years ago when they were between 16-26 years of age at the time of the first dose)

Table 2. Summary of anti-HPV GMTs at baseline, and 7 and 30 days post-booster dose (cLIA)

Antibodies (cLIA)	Group 1 (2-dose girls)		Group 2 (3-dose girls)		Group 3 (3-dose women)		GMT ratio (95% CI)		
	n	GMT (95% CI)	n	GMT (95% CI)	n	GMT (95% CI)	2-dose girl/3-dose girl	2-dose girl/3-dose women	3-dose girl/3-dose women
Baseline									
HPV 6									
HPV 11									
HPV 16									
HPV 18									
At 7 days post-booster dose									
HPV 6									
HPV 11									
HPV 16									

HPV 18									
At 30 days post-booster dose									
HPV 6									
HPV 11									
HPV 16									
HPV 18									

Table 3. Summary of anti-HPV GMTs at baseline, and 7 and 30 days post-booster dose (total IgG)

Antibodies (IGG)	Group 1 (2-dose girls)		Group 2 (3-dose girls)		Group 3 (3-dose women)		GMT ratio (95% CI)		
	n	GMT (95% CI)	n	GMT (95% CI)	n	GMT (95% CI)	2-dose girl/3-dose girl	2-dose girl/3-dose women	3-dose girl/3-dose women
Baseline									
HPV 6									
HPV 11									
HPV 16									
HPV 18									
At 7 days post-booster dose									
HPV 6									
HPV 11									
HPV 16									
HPV 18									
At 30 days post-booster dose									
HPV 6									
HPV 11									
HPV 16									
HPV 18									

Table 4. Summary of HPV seropositivity at baseline, and at 7 and 30 days post-booster dose (cLIA)

Antibodies (cLIA)	Group 1 (2-dose girls)			Group 2 (3-dose girls)			Group 3 (3-dose women)		
	n	% seropositive (95% CI)	n	% seropositive (95% CI)	n	% seropositive (95% CI)	n	% seropositive (95% CI)	
Baseline									
HPV 6									
HPV 11									
HPV 16									

HPV 18						
At 7 days post-booster dose						
HPV 6						
HPV 11						
HPV 16						
HPV 18						
At 30 days post-booster dose						
HPV 6						
HPV 11						
HPV 16						
HPV 18						

Table 5. Summary of HPV seropositivity at baseline, and 7 and 30 days post-booster dose (total IGG)

Antibodies (IGG)	Group 1 (2-dose girls)		Group 2 (3-dose girls)		Group 3 (3-dose women)	
	n	% seropositive (95% CI)	n	% seropositive (95% CI)	n	% seropositive (95% CI)
Baseline						
HPV 6						
HPV 11						
HPV 16						
HPV 18						
At 7 days post-booster dose						
HPV 6						
HPV 11						
HPV 16						
HPV 18						
At 30 days post-booster dose						

HPV 6						
HPV 11						
HPV 16						
HPV 18						

Table 6. Difference in anti- HPV GMTs between baseline vs. at 7 and 30 days post-booster dose of HPV vaccine (cLIA)

Antibodies (cLIA)	Group 1 (2-dose girls)		Group 2 (3-dose girls)		Group 3 (3-dose women)		Group 1 vs 2	Group 1 vs 3	Group 1 vs 3
	Log Difference	P Value	Log Difference	P value	Log Difference	P value	P-value for difference between differences for group 1 vs 2	P-value for difference between differences for group vs 3	P-value for difference between differences for group 1 vs 3
Baseline vs. 7 days post-booster dose of HPV vaccine									
HPV 6									
HPV 11									
HPV 16									
HPV 18									
Baseline vs. 30 days post-booster dose of HPV vaccine									
HPV 6									
HPV 11									
HPV 16									
HPV 18									

Table 7. Difference in anti- HPV GMTs between baseline vs. at 7 and 30 days post-booster dose of HPV vaccine (total IgG)

Antibodies (IGG)	Group 1 (2-dose girls)		Group 2 (3-dose girls)		Group 3 (3-dose women)		Group 1 vs 2	Group 1 vs 3	Group 1 vs 3
	Log Difference	P Value	Log Difference	P value	Log Difference	P value	P-value for difference between differences	P-value for difference between differences for group	P-value for difference between differences
Baseline vs. 7 days post-booster dose of HPV vaccine									
HPV 6									
HPV 11									
HPV 16									
HPV 18									
Baseline vs. 30 days post-booster dose of HPV vaccine									
HPV 6									
HPV 11									
HPV 16									
HPV 18									

							for group 1 vs 2	vs 3	for group 1 vs 3
Baseline vs. 7 days post-booster dose of HPV vaccine									
HPV 6									
HPV 11									
HPV 16									
HPV 18									
Baseline vs. 30 days post-booster dose of HPV vaccine									
HPV 6									
HPV 11									
HPV 16									
HPV 18									

Tables for uploading results to ClinicalTrials.gov, as required.
